Screening and Session 1. See Table 1. Interested individuals will telephone the laboratory, and trained, supervised research assistants will assess inclusion and exclusion criteria via interview. Eligible participants will be scheduled for Session 1, which will last about one hour. Upon arrival, participants will provide informed consent, will be screened again for eligibility, and complete baseline measures. For screening purposes, participants will complete the Symptom Checklist-90-Revised (SCL-90-R; self-report measure of psychiatric symptomatology)³¹, the Paykel Suicide Scale³², and an adaptation of the telephone screening interview (to re-assess for exclusionary criteria). The Paykel Suicide Scale was selected given its ability to be modified for select periods and ease of comparison across study assessments. Participants who report a score of 65 or more on the SCL-90-R (i.e., indicative of significant psychiatric symptomatology) or current suicidal ideation will be excluded (and given appropriate referrals). Participants will also complete the Alcohol Use Disorders Identification Test (AUDIT³³), which will be utilized to provide personalized alcohol use psychoeducation and treatment referrals. Per AUDIT recommendations and the ethical guidelines of alcohol administration research, all participants will receive literature focused on the reduction of hazardous drinking at the end of the study.

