Session 2. Participants who remain eligible will be scheduled for a second appointment, which will be one to ten hours in duration, depending on their randomly-assigned condition (i.e., alcohol vs. placebo). When scheduling Session 2, participants will be told to refrain from drinking alcohol or using recreational drugs 24 hours prior to the session and to refrain from eating four hours prior to the session. Upon arrival at the laboratory, eligibility will be confirmed, including a breathalyzer test to ensure a zero BrAC and field sobriety test for comparison post-detoxification. Those with nonzero BrAC will be rescheduled. Female participants will be given a pregnancy test kit and asked to produce a urine sample in a private bathroom located adjacent to

the laboratory (those with positive tests will be excluded). Height and weight will be measured to calculate alcohol dosage. We will assess pre-manipulation mood via the Positive and Negative Affect Schedule-Expanded Form (PANAS-X)–sadness, guilt, and joviality subscales³⁸ and 2-item Brief Hopelessness Measure.³⁹

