Manipulation Check and Dependent Variable Measurement: After the mood induction, participants will complete the PANAS-X subscales as a manipulation check (<2 min). Participants will then complete a Stroop⁴⁷ task modified to assess attention towards suicide-related cues (i.e., Suicide Stroop³). This modified Stroop task is a performance-based measure conducted via computer that documents response latencies on identification of the colors of words presented on the screen. Neutral (museum, paper, engine), negative (alone, rejected, stupid), positive (happy, success, pleasure), and suicide-related (suicide, dead, funeral) categories of words are presented, and greater response latencies indicate greater interference of the semantic content in naming the color. Participants will be instructed to indicate the word color as guickly and accurately as possible using red and blue keys. Stimuli will be presented using Empirisoft DirectRT software.⁴⁸ Trials will be presented in a random order to each participant. Interference for suicide-related words (i.e., suicide-related attentional bias) will be calculated by subtracting the response latencies for neutral words from the latencies for suicide-related words.³ Internal consistency coefficients for reaction time tasks like Stroop tasks are typically low⁴⁹⁻⁵⁰, and it has been suggested that using internal consistencies from past studies is inadvisable as sample characteristics can have a significant impact on the internal consistency.⁴⁹ Nonetheless, in our partial test, the internal consistencies for the interference scores (using a split-half coefficient) and the suicide trial reaction times were .49 and .86, respectively, which are typical of Stroop tasks⁵⁰⁻⁵¹ and much better than reliabilities in prior studies using the Suicide Stroop.²⁸ The Suicide Stroop has demonstrated construct validity through associations with past and future suicidal behavior.^{3,21} Thus. It serves as the primary outcome

of interest. Following the Stroop, participants will complete the 2-item Brief Hopelessness Measure³⁹ (a secondary outcome, see *Potential Problems* below).

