Pre-Manipulation Mood and Cognition (PANAS-X; Brief Hopelessness Measure)
Manipulation Procedures and Checks
Alcohol or placebo administration; Post drinking BrAC measurement; Manipulation check
Mood induction (positive or negative); Manipulation check: PANAS-X
Outcome Measure: Modified Stroop-Suicide (primary outcome of interest), Brief Hopelessness Measure
Post-Study Procedures: Detoxification (if applicable); Post-Study Verbal Interview, Paykel Suicide Scale
(current; risk screening for post study interview), Debriefing, Payment
Follow up Wollness Check Dhone Calle (day of day following, and wook following)

Follow-up Wellness Check Phone Calls (day of, day following, and week following)

Analytic plan

H1: We will quantify the number of individuals screened and the percentage who are eligible and participate. We will run descriptive statistics to quantify 1) prevalence of successful mood induction, 2) distress ratings post-study session, and 3) number of adverse events. Using measures of effect size, t-tests, and Chi square analyses, we will examine sociodemographic differences in these feasibility factors. H2: We will use measures of effect size, t-tests, and Chi Square analyses to examine sociodemographic differences in suicide-related attentional bias scores. H3: The interactive effect of mood and AUA on suicide-related attentional bias will estimated model be using а general linear of the form $\hat{Y} = \beta_0 + \beta_1 Alcohol + \beta_2 Mood + \beta_3 Alcohol \times Mood$. **H4:** The interactive effect of alcohol expectancies and AUA on suicide-related attentional bias will be estimated using a general linear model of the form $\hat{Y} = \beta_0 + \beta_1 Alcohol + \beta_2 Expectancies + \beta_3 Alcohol \times Expectancies$. For H3 and H4, we will use linear contrasts to estimate effects. Inferences will be conducted using 68% CIs for comparisons of interest, as significance testing is not a primary study aim. See Statistical Design and Power attachment.

Potential Problems, Alternative Strategies, Benchmarks for Success, and Impact

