Given this is the first known project to examine the effects of AUA, mood, and expectancies on suicide-related attentional bias, our ongoing partial test of the proposed study includes another suicidal bias measure: the Implicit Associations Task-Life/Death (IAT-SI⁴), which measures implicit suicidal cognition. Scores indicate level of identification with life versus death and correlates with suicidal behavior.⁴ We will replace the Stroop with this task if our partial test of the reveals that the mood induction influences IAT-SI scores but not Stroop scores. Even if our proposed pilot study does not find effects of AUA, mood, and expectancies on suicide-related attentional bias, we have a post-manipulation measurement of hopelessness—a strong risk factor for suicide. This secondary dependent variable could serve as the basis for an R01. If in our 10 pre-pilot subjects, the mood induction fails >50% of the time, we will use another effective mood induction (i.e., imaginative film). Further, we are oversampling by 25% (150 subjects instead of 120, in case of 25% mood induction failures). Finally, although our proposed sample may not generalize to suicidal individuals, we believe any effect found in the present study will be larger in a sample of suicidal individuals. This study's strong internal validity offers a strong basis for future studies of individuals with higher levels of distress. Impact. If hypotheses are supported, it would provide strong support for the AAM as it applies to suicide risk. Future studies could test whether decreasing the salience of negative mood or suicide-related expectancies reduces suicide-related attentional bias and thus suicide risk. Possible downstream implications include the potential to inform future basic and applied research examining the effects of AUA on suicide risk. Finally, this project will provide me with the relevant experience to conduct future experiments using alcohol administration to investigate behavioral and affective consequences of AUA.

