COVER PAGE

Official Study Title: Acute Use of Alcohol and Attentional Bias Towards Suicide: An Experimental Test of the Attention-Allocation Model

NCT number: NCT04276779

Date of the document: December 1, 2023

Statistical Design and Power

Statistical Design

Data from Qualtrics (Session 1 baseline data), excel (paper data entered from Session 1 and 2), and DirectRT software will be exported into IBM SPSS statistical software, Version 25. Standard data quality checks and cleaning procedures will be completed. Most notably, any participants voicing awareness of the study aims or not responding adequately to the mood induction will be removed from the initial analyses. Second, manipulation checks will be performed by comparing the participants in the mood conditions on self-reported mood post-manipulation. We expect that negative mood participants will have greater mean scores on the guilt and sadness subscales and lower mean scores on the joviality subscale compared to the positive mood participants.

Study variables for the entire sample will be examined using descriptive statistics such as frequencies and percentages (for categorical variables) and means, standard deviations, and ranges (for continuous variables) to ensure values are reasonable. Prior to conducting analyses related to the hypotheses of the study, individual distributions of continuous variables will be examined visually with histograms to confirm that all assumptions for the analyses are reasonably met. Methods robust to distributional assumptions will be used as appropriate.

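### Does the lack of a written analysis for hopelessness, the secondary outcome held in reserve if the Stroop shows nothing, call for a change to the plan?

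*Protocol*

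**What the plan says.** The Protocol's section on the manipulation check and dependent variable states that, after the Stroop, "participants will complete the 2-item Brief Hopelessness Measure", and labels it a secondary outcome. Potential Problems gives it a reserve role: if the pilot "does not find effects of AUA, mood, and expectancies on suicide-related attentional bias, we have a post-manipulation measurement of hopelessness". It adds: "This secondary dependent variable could serve as the basis for an R01".

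The measure is scheduled twice. Session 2 lists the PANAS-X subscales "and 2-item Brief Hopelessness Measure" before beverages are served. Table 1 repeats this, and places the second reading in the row "Outcome Measure: Modified Stroop-Suicide (primary outcome of interest), Brief Hopelessness Measure".

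No analysis is attached to it. The Protocol's Analytic plan covers feasibility (H1) and suicide-related attentional bias (H2 to H4). The SAP does not name hopelessness. Its Hypothesis 3 and 4 models take the Stroop interference score as outcome, with no baseline covariate, and its pre-manipulation check covers sadness, guilt and joviality only. The SAP text that can reach hopelessness is general: descriptive statistics for study variables, inspection of distributions, and the statement "Methods robust to distributional assumptions will be used as appropriate".

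**The concern.** An outcome named in advance for use when the primary one shows nothing is the kind whose analysis should not be picked after the results are in. Copying the Hypothesis 3 model does not settle everything. No pre-manipulation Stroop is scheduled, so that model never had to deal with a baseline score. Hopelessness has one, and it could be ignored, subtracted or adjusted for. These options give intervals of different width and can give different answers from the same data.

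The stake would be the precision and credibility of a hopelessness result offered in support of a larger grant. The primary analysis is not touched.

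**Working it through.** **Inputs from the SAP, Power and Sample Size Considerations.** n = 30 per condition combination, σ = 1 (standardised score), 68% intervals. The multiplier is z(.84) = .9945.

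**The plan's own figures (Stroop).**
- Alcohol effect within a mood group: .9945 × √(2/30) = .9945 × .2582 = .257 (stated .26).
- Alcohol × Mood interaction: .9945 × 2/√30 = .9945 × .3651 = .363 (stated .36).

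Both reproduce. Neither document gives a figure for hopelessness, so carrying this yardstick over is an extension.

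**Sample size for hopelessness.** In the partial test reported under Preliminary Data, 6 of 34 participants were lost to mood-induction or deception failure. The other listed losses (Stroop software, error trials) do not bear on a questionnaire. Retaining 28 of 34 gives 150 × 28/34/4 = 30.9 per cell and an interaction half-width of .9945 × 2/√30.9 = .36. A flat 25% loss gives 150 × .75/4 = 28.1 per cell and .38. Thirty per cell is a fair working value.

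**What the choice of analysis does to precision.** The documents give no pre-post correlation, so r = .3, .5 and .7 are assumed, with N = 120.
- Adjusted against post score, SE ratio = √[(1 − r²)(1 + 1/(N − 6))].
- Change against post score, equal variances assumed, SE ratio = √[2(1 − r)].

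| r | Adjusted ratio | Adjusted half-width | Change ratio | Change half-width |
|---|---|---|---|---|
| .3 | .958 | .363 × .958 = .348 | 1.183 | .363 × 1.183 = .430 |
| .5 | .870 | .363 × .870 = .316 | 1.000 | .363 |
| .7 | .717 | .363 × .717 = .260 | .775 | .363 × .775 = .281 |

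Adjustment therefore cuts the SE by 4%, 13% or 28%. If r = 0 it costs √(1 + 1/114) − 1 = 0.4%.

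**How firm these figures are.** The measure has two items, and the sample is screened for low distress (the sentence beginning "Participants who report a score of 65 or more on the SCL-90-R" describes an exclusion), so many answers may sit at the floor. In a simulated check with two five-point items, squared item loading .6 and 40–75% of answers at the floor (all assumed), a true correlation of .7 appears as .47 down to .40. Then √(1 − .47²) = .883 and √(1 − .40²) = .917, a gain of about 8–12%.

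The change-score column depends on equal variances. If the pre-score SD is 0.7 of the post-score SD (assumed), the ratio is √(1 + .49 − 1.4r) = 1.034, .889 and .714: +3%, −11% and −29% instead of +18%, 0% and −23%.

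**Free choice among the three.** Simulation with no true effect, 30 per cell and 20,000 trials per correlation:
- Any single 68% interval for the interaction excludes zero in about 32% of trials, as its level implies.
- At least one of the three does so in about 50–53% with equal variances, and in 46–48% if the pre-score SD is 0.7 of the post-score SD.

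**The case for a change.** The case for amending the plan is respectable. The gap is in the text and does not depend on interpretation. The reserve role is stated in the Protocol itself, and it comes into play when the Stroop result is already known. The general SAP wording on descriptives and robust methods names no comparison and no use of the pre-score. The separate contingency in Potential Problems, swapping the Stroop for an implicit-association task, is decided from the partial test and does not fill the gap. A remedy would be one paragraph, with no new data and a worst-case SE penalty of 0.4%.

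The omission stands, and so does the rise above 32% under free choice, which appears in every setting tried. Three things limit what follows.

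- The excess is measured by whether a 68% interval excludes zero. The plan uses these intervals to show plausible effect sizes and says significance testing is not its aim. Even one analysis fixed in advance would exclude zero in 32% of null trials.
- The precision gain rests on an assumed correlation, and is modest if floor effects are as strong as supposed.
- A remedy is less simple than it looks. Reusing the Hypothesis 3 analysis set would apply the Stroop latency and error-rate exclusions to a self-report scale for which they have no evident meaning. A model in alcohol and mood alone would leave out expectancies, which the quoted sentence also mentions.

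**Conclusion.** No change is needed. The plan leaves out a detail; it does not state a wrong one. Both scores are scheduled, and the pre-score precedes both manipulations. Post-score, change-score and baseline-adjusted analyses are all valid comparisons of randomised groups. An analyst with a baseline reading from the same session and the Hypothesis 3 model to hand would probably adjust for it.

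On the assumed correlations of .3 to .7, the interaction half-width at 30 per cell lies between .26 and .35 SD with adjustment, against .36 with the post score alone. A change score spans .28 to .43 under equal variances. That spread concerns an exploratory secondary outcome outside the four hypotheses, in a pilot that makes no confirmatory claim for it. Stating the choice beforehand would be tidy, at low priority. Its absence means only that a hopelessness result should be read as exploratory, which is already its place in this study.

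The conclusion rests on that status. It would be different if hopelessness carried a hypothesis or a decision rule.

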COVER PAGE

Official Study Title: Acute Use of Alcohol and Attentional Bias Towards Suicide: An Experimental Test of the Attention-Allocation Model

NCT number: NCT04276779

Date of the document: December 1, 2023

Statistical Design and Power

Statistical Design

Data from Qualtrics (Session 1 baseline data), excel (paper data entered from Session 1 and 2), and DirectRT software will be exported into IBM SPSS statistical software, Version 25. Standard data quality checks and cleaning procedures will be completed. Most notably, any participants voicing awareness of the study aims or not responding adequately to the mood induction will be removed from the initial analyses. Second, manipulation checks will be performed by comparing the participants in the mood conditions on self-reported mood post-manipulation. We expect that negative mood participants will have greater mean scores on the guilt and sadness subscales and lower mean scores on the joviality subscale compared to the positive mood participants.

Study variables for the entire sample will be examined using descriptive statistics such as frequencies and percentages (for categorical variables) and means, standard deviations, and ranges (for continuous variables) to ensure values are reasonable. Prior to conducting analyses related to the hypotheses of the study, individual distributions of continuous variables will be examined visually with histograms to confirm that all assumptions for the analyses are reasonably met. Methods robust to distributional assumptions will be used as appropriate.

Prior to analysis, Suicide Stroop scores will be evaluated for outliers. We will exclude: trials with incorrect responses, trials with response latencies ± 2 SD from each participant's mean response latency, participants with a mean response latency ± 2 SD from the overall sample's mean, participants whose error rate was +2 SD above the error rate for all participants. We will also examine the reliability, factor structure, and concurrent validity for the suicide-related alcohol expectancies measure (created for this study) prior to its use for Hypothesis 3. We will use exploratory factor analysis (with parallel analysis), Cronbach's alpha, and examine associations with AUDIT total scores and past suicidal ideation severity. Finally, we will confirm there were no pre-existing relevant differences in mood states between our mood and alcohol conditions by estimating measures of association (i.e., R²) between condition assignment and pre-manipulation sad, guilty, and joviality mood states.

Pre-Pilot tests: To finalize study procedures, for the 10 pre-pilot subjects, we will examine prevalence of mood induction effectiveness. If >50% fail the mood induction, we will replace it with another effective mood induction (imaginative film). We will also run frequencies to examine percentage of participants who are successfully deceived, expecting these percentages to be high (>90%). We will use these results to adjust the protocol in order to improve success of our mood manipulation and deception.

Specific Aim 1, Hypothesis 1a: To test the feasibility our experiment, we will first quantify the number of individuals who contact our lab about the study and the percentage who are eligible and participate. We will run descriptive statistics to quantify 1) prevalence of successful mood induction (expecting at least 75%), 2) distress ratings after the study session (expecting average ratings to be low), and 3) number of adverse events (expecting less than 1% of pilot subjects). **Objective 1b:** Using measures of effect size (i.e., Cohen's d, Cramer's V) and t-tests and Chi square analyses, we will examine sociodemographic differences (gender, age, race/ethnicity, income, and alcohol use history) in these feasibility factors.

Specific Aim 2, Hypothesis 2: Examine sociodemographic differences in suicide-related attentional bias. Suicide-related attentional bias will be higher among women, individuals with lower income, individuals ages 21-34, and individuals with heavier alcohol use than their comparators. Although racial differences are not observed in suicide attempts, we will explore racial differences in suicide-related attentional bias.

Analysis: Using measures of effect size and *t*-tests and Chi Square analyses where appropriate, we will examine potential these sociodemographic differences in suicide-related attentional bias scores.

Specific Aim 3, Hypothesis 3: Examine the conditional effect of AUA on suicide-related attentional bias by mood states. Individuals in the alcoholic beverage-negative mood condition will exhibit the greatest suicide-related attentional bias, followed by individuals in the placebo beverage-negative mood condition, placebo beverage-positive mood condition, and alcoholic beverage-positive mood condition.

Analysis: The interactive effect of mood and alcohol (Alcohol X Mood Induction) on attentional bias towards suicide-related cues (Stroop interference score, calculated by subtracting the response latencies for neutral words from the latencies for suicide-related words) will be estimated using a general linear model of the form $\hat{Y} = \beta_0 + \beta_1 Alcohol + \beta_2 Mood + \beta_3 Alcohol \times Mood$, where \hat{Y} is the average Stroop interference score, *Alcohol* is a binary indicator (1=yes, 0=no) of assignment to alcoholic beverage intake, and *Mood* is a binary indicator of assignment to the positive vs. negative mood induction (1 vs. 0). Among the positive mood induction group, the average effect of alcohol intake on Stroop interference scores is estimated by the sum of coefficients $\beta_1 + \beta_3$, while the average effect of alcohol intake in the negative mood induction group is estimated by the coefficient β_1 . Therefore, the coefficient β_3 estimates the differential effect of alcohol intake conditional on mood induction. We will use model-predicted means to estimate mean Stroop interference scores among the negative mood-alcohol condition participants. Measures of effect size (e.g. R², partial eta², Cohen's d) will be used to aid in interpretation. Inferences will be conducted using confidence intervals for the comparisons of interest, as statistical significance testing is not the primary goal of the study.

Specific Aim 4, Hypothesis 4: Explore the conditional effect of AUA on suicide-related attentional bias by alcohol expectancies. The relation of suicide-related alcohol expectancies with suicide-related attentional bias will be stronger among those in the AUA condition compared to those in the placebo condition.

Analysis: The interactive effect of expectancies and alcohol (Alcohol X Expectancies) on attentional bias towards suicide-related cues (Stroop interference score, calculated by subtracting the response latencies for neutral words from the latencies for suicide-related words) will be estimated using a general linear model of the form $\hat{Y} = \beta_0 + \beta_1 Alcohol + \beta_2 Expectancies + \beta_3 Alcohol \times Expectancies$, where \hat{Y} is the average Stroop

interference score, *Alcohol* is a binary indicator (1=yes, 0=no) of assignment to alcoholic beverage intake, and *Expectancies* is a continuous score of alcohol expectancies (higher scores indicate higher expectancies). The coefficient β_2 estimates the differential effect of expectancies conditional on alcohol intake. With the model, we

will estimate Stroop inference scores by alcohol conditions at the mean expectancy and ± 1 SD away from the mean, expecting that in the alcohol condition, expectancies will have a stronger association with attentional bias towards suicide scores. Measures of effect size (e.g. R², partial eta², Cohen's r) will be used to aid in interpretation. Inferences will be conducted using confidence intervals for the comparisons of interest.

Power and Sample Size Considerations

For this training grant, as a compromise between feasibility and precision of estimates, I propose to recruit 10 pre-pilot subjects and 150 subjects (approximately 38 per condition combination) over a 2.5-year period. Assuming that 25% of subjects may be excluded due to mood induction failure, we will have 30 subjects per condition. Rather than traditional significance testing, the goal of the project is to examine feasibility and tolerability of procedures and explore observed effect sizes. Inference will be conducted primarily by estimation of 68% confidence intervals to be used as reasonable ranges for observed effect sizes. Following the proposed analysis of Hypothesis 3, it can be shown using variance algebra that the standard error of the effect of alcohol intake on Stroop interference scores within each of the mood induction groups (positive or negative) is $SE_{Alco.Eff} = \sigma \sqrt{2/n}$, where σ is the standard deviation of the Stroop interference scores and *n* is the sample size per condition combination. Thus, the standard error of the differential effect of alcohol intake conditional on mood induction (i.e. the interaction term) is $SE_{Diff.Alco.Eff} = 2\sigma/\sqrt{n}$. With n = 30 and standardizing the Stroop interference scores (i.e. $\sigma = 1$) to express the confidence interval in terms of an effect size (Cohen's d), the half width of a 68% confidence interval for the standardized effect of alcohol intake within each of the mood induction groups is .26 and the half width of a 68% confidence interval for the standardized differential effect of alcohol intake conditional on mood induction is .36, which provide reasonable and tolerable uncertainty ranges.

For completeness, in terms of null hypothesis significance testing (not a primary goal of this study), at a significance level of .05 the sample size provides 80% power to detect a standardized effect of alcohol intake

within each of the mood induction groups of .72, and standardized differential effect of alcohol intake conditional on mood induction of 1.

Individually Randomized Group-Treatment Trial Consideration: Note that this is an experimental design that randomizes participants to groups (alcohol or placebo and negative mood or positive mood induction). Participants will experience these manipulations independently (i.e., participants will not be interacting with one another). Nonetheless, the same research personnel will likely carry out the mood induction and alcohol administration manipulations with several different participants. Thus, some may designate this research as an "Individually Randomized Group-Treatment Trial," given the potential for nested data within research personnel. Because the mood induction and alcohol administration procedures are significantly standardized, we do not expect the effectiveness of these manipulations to vary across research personnel. However, we will collect data on who administers these protocols and examine differences across personnel to validate this assumption. If significant variation is discovered, we will *employ fixed effects* to account for these issues.
